1. Participants will then be randomized to the intervention or usual care arm with probability equal to 1/2 (i.e., 1:1 randomization) using a computerized random number generator in blocks (size < 10; all study personnel except the statisticians are blinded to block size). The randomization assignment will be revealed to the patient by the un-blinded researcher. If the patient is randomized to the intervention, he/she will be shown the educational video the same day. The educational video is an 18 minute video that describes the risks of obesity and explores the three weight management options available to patients with severe obesity (BMI ≥ 35) in the VA. The video explains the weight loss treatments the VA offers, how to access them, what eligibility criteria patients might have to meet to obtain them, and describes the typical health outcomes for each treatment. Patients will also hear stories from Veterans who went through one particular treatment option. Patients randomized to usual care will not be shown the educational video.
2. Patients will be asked to complete a post-assessment within 7-14 days of their MOVE! visit. Patients randomized to the intervention arm will also be asked to participate in a 10-minute interview in addition to the post-intervention assessment. The post-intervention assessment and interview (intervention arm only) will be scheduled prior the patient's MOVE! visit. This post-assessment will be completed over the phone approximately 7-14 days after their MOVE! visit. Veterans may be reminded of this call via text message, phone call, or email prior to their appointment. They may also opt out of receiving a reminder. All email communications will come from a researcher's VA email account. Following their post-assessment call (and regardless of whether they complete their post-assessment call), a monetary incentive will be provided to participants for their time (\$50).

Measures: Demographic data will be collected at baseline, prior to learning of randomization assignment. Signal of effect (patient outcomes), intervention fidelity, acceptability of the intervention, and feasibility measure will be collected during the pre- and/or post-intervention period as outlined in **Table 1**.

Table 1: Measures for Pilot Testing (Pre and Post-Intervention)

[figure not shown]
Measure	Pre	Post	Reliability	Validity	Group
Patient Demographics	X		N/A	N/A	Both
Patient Outcomes					

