Primary patient outcome: Behavioral intentions in pursuing any of the 3 treatment options in the VA		X			Both
Secondary patient outcome #1: Preparation for Decision-making Scale (10 Qs) ³		X	$\alpha=0.92-0.96^3$	Scores correlated with the informed ($r=0.21; p<.01$) and support ($r=0.13, p=.01$) DCS subscales ³	Both
Secondary patient outcome #2: Patient knowledge and attitudes (Informed Choice; 12 Qs) ⁴		X	$\alpha=.82^4$	Mean knowledge score correlated with responses to open-ended questions designed to elicit their understanding of the test ⁴	Both
Secondary patient outcome #3: Self-efficacy measure		X	N/A	N/A	Both
Secondary patient outcomes #4: Process and outcome measures, including patient checked the box for bariatric surgery or requested to go down the bariatric pathway or patient checked the box for MOVE! visits or requested to go down the MOVE! pathway; attending MOVE! bariatric visit, info session, bariatric referral, bariatric visit, bariatric surgery, bariatric outcomes		X	N/A	N/A	Both
Acceptability					
Acceptability to patients: Qualitative interview		X	N/A	N/A	Intervention only
Feasibility					
Recruitment and Attendance Rates	X	X	N/A	N/A	Both
ICC=Intra-class correlation coefficient; IRA=inter-rater agreement					

1. Patient demographics: Baseline patient demographics including age, gender, sex, race, BMI, comorbidities, pregnancy status (if female), and contact information will be obtained from the electronic health record.

2. Primary patient outcome - Behavioral intentions: Behavioral intentions to pursue bariatric surgery or treatment in the MOVE! program will be assessed separately with five semantic differential items ranging from 1 to 7 (unlikely to likely; not possible to certain) following the methods of Azjen.⁸

3. Secondary patient outcome - Preparation for decision-making: Patients will complete the Preparation for Decision-making questionnaire which consists of 10-items that assesses the patient's opinion about the effect of the educational video had on his/her decision (e.g. "Did this educational material help you think about which pros and cons are most important").⁹

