6. Process measures: We will record whether patients “checked” the bariatric surgery MOVE! visit box in their MOVE! intake form. We will record whether patients attended a MOVE! bariatric visit, attended a bariatric surgery info session, received a bariatric referral, attended a bariatric surgery visit, underwent bariatric surgery, and lost weight after bariatric surgery. We will also track the number of MOVE! visits the patient has as well as any change in weight. These variables will be obtained from a data pull from the Corporate Data Warehouse (VA Database) at the end of the study.

7. Acceptability to patients (patient interviews): Acceptability of the educational video to patients will be assessed during a 10 minute semi-structured interview that will be conducted during the post-intervention assessment phone call for patients in the intervention arm. The patient will be asked several questions about use of the educational video, including the extent to which the amount of information presented was appropriate, clear, and in hindsight, the ideal timing of administration of the educational video. Patients who complete the intervention via VVC will be asked questions about their experience using the VVC system.

8. Feasibility of recruitment: Feasibility will be assessed by measuring recruitment and retention rates. The recruitment rate is defined by the number of Veterans who indicate, during a recruitment phone call, that they will participate divided by the number reached. Reasons for declining will be captured and analyzed for future study design optimization. The retention rate is defined as the number who watch the video and complete all assessments, divided by the number scheduled. A priori feasibility targets are $\geq 60\%$ recruitment and $\geq 80\%$ retention.

Data analysis and sample size: Descriptive statistics will be used to characterize patient demographics, secondary patient outcomes, and acceptability by group. Analysis of the primary outcome will treat pre- and post-intervention outcomes as two repeated measures on each subject. The regression model will include a post-visit indicator, an intervention group indicator, and an interaction between the two, the coefficient of which will be the parameter of interest capturing the intervention effect. To account for the repeated measures within patient, the model will include a random patient effect.

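### The primary model needs a baseline measure of behavioral intentions that Table 1 does not schedule

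*Combined protocol and SAP*

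**What the plan says.** All references are to section II of the combined protocol and SAP.

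- **Data analysis and sample size.** "Analysis of the primary outcome will treat pre- and post-intervention outcomes as two repeated measures on each subject". The regression has a post-visit indicator, a group indicator and "an interaction between the two, the coefficient of which will be the parameter of interest capturing the intervention effect". It continues: "To account for the repeated measures within patient, the model will include a random patient effect". The same section wants the pilot to supply estimates of within- and between-subject variability.
- **Table 1.** The row "Primary patient outcome: Behavioral intentions in pursuing any of the 3 treatment options in the VA" has a single X, in the Post column, for both groups. Its Reliability and Validity cells are blank.
- **Measures, item 2.** "Behavioral intentions to pursue bariatric surgery or treatment in the MOVE! program will be assessed separately with five semantic differential items". No time point is given.
- **Measures, opening paragraph.** "Demographic data will be collected at baseline, prior to learning of randomization assignment". The outcome and feasibility measures "will be collected during the pre- and/or post-intervention period as outlined in" Table 1.
- **Study Procedures.** Before randomisation the patient gives consent, signs the HIPAA form and completes a demographic survey. The post-assessment is a phone call about 7-14 days after the MOVE! visit. The intention items are not named at either point.
- **Study design.** Patient outcomes are said to be assessed both before and after the video, following Table 1.

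**The concern.** The analysis section and the measurement schedule describe two different data sets. The model needs two intention scores per patient, and the schedule provides one. This is the only regression model the plan specifies, it is for the primary patient outcome, and the plan singles out one coefficient in it as the intervention effect.

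If site staff work from Table 1, that coefficient cannot be obtained, and neither can the within-subject variability of this outcome that the follow-on trial would use. The gap cannot be repaired at analysis: once a patient has seen the video or the visit has passed, the baseline is gone.

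**Working it through.** The plan gives no power calculation, effect size or SD, so there is no stated figure to reproduce. The question is whether the stated model can be fitted to the scheduled data.

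**Inputs.** Up to 40 patients randomised 1:1, so 20 per arm (Data analysis and sample size; Study Procedures). Model terms are from Data analysis and sample size. Timing is from Table 1.

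**1. What Table 1 marks.** It has 8 measure rows. Demographics is marked Pre only, and recruitment and attendance rates are marked in both columns, so the Pre column is in use. None of the 5 patient-outcome rows has a Pre mark. All 8 rows split into the same six cells in the extracted text, so a shifted column is unlikely, although the PDF layout could not be seen.

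**2. Fixed effects.** The model is E(Y) = b0 + b1·post + b2·group + b3·post×group, which gives four cell means:

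- usual care, pre: b0
- usual care, post: b0 + b1
- video, pre: b0 + b2
- video, post: b0 + b1 + b2 + b3

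Hence b3 = (video post − video pre) − (usual care post − usual care pre). It needs all four cells.

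With post scores only, post = 1 in every row. The post column then equals the intercept column, and the post×group column equals the group column. Only b0 + b1 and b2 + b3 can be estimated. The sum b2 + b3 is the between-arm difference in post scores; b3 alone is not estimable.

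| Data available | Rows | Rank (of 4) | b3 estimable |
|---|---|---|---|
| Post only (Table 1) | 40 | 2 | no |
| Post for all, baseline in the video arm only | 60 | 3 | no |
| Post for all, one baseline in each arm | 42 | 4 | yes |
| Pre and post for all (analysis section) | 80 | 4 | yes |

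**3. Variance components.** The covariance is V = τ²ZZ′ + σ²I, with τ² the patient variance and σ² the residual variance. With one score per patient ZZ′ = I, so V = (τ² + σ²)I and only the sum is identifiable (1 of 2 parameters). With two scores per patient, the two scores have covariance τ² and each has variance τ² + σ², so both parameters are identifiable (2 of 2).

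**4. Precision of what survives.** At 20 per arm the post-score difference has SE = √(2/20) = 0.316 SD. At 80% retention (16 per arm) it is √(2/16) = 0.354 SD. The interaction has SE = √[(2/20)·2(1 − ρ)], where ρ is the pre-post correlation. The documents do not give ρ. Assuming a range of 0.3 to 0.8 and equal SDs at both times, the SE is 0.374 SD at ρ = 0.3, 0.316 at 0.5 and 0.200 at 0.8.

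**The case against.** The strongest reply is that a baseline was clearly intended and someone forgot a Pre mark. The Study design paragraph speaks of assessment before and after the video, and Patient Outcomes is the Table 1 heading under which behavioral intentions sits. The title of Table 1 mentions both periods. The primary-outcome row is the only one of 8 with blank Reliability and Validity cells, so it looks unfinished. The retention definition refers to all assessments, the sample-size text refers to change, and the Data and Safety Monitoring Plan loosely mentions assessments in private rooms, where the only such meeting described is the one at enrolment. The silence of Study Procedures is also weak evidence, since it does not name the intention items at the post call either.

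Much of this stands, and an omitted mark is plausible. It does not resolve the conflict. The Study design and Measures paragraphs both send the reader back to Table 1, which says Post only. The other phrases are not specific to this outcome. Even a clerical omission leaves staff with no instruction to collect the baseline.

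A second reply is that little is lost. The plan disclaims significance testing, and feasibility and acceptability come first. Under randomisation the post-score difference targets the same intervention effect, and step 4 shows it is more precise than the interaction whenever ρ is below 0.5. That stands too, and it limits the harm. But the post-score difference is not the analysis the plan states, and it gives no within-subject variance.

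**Conclusion.** The concern holds. Followed as written, Table 1 makes the stated primary model unfittable: rank 2 of 4, the named parameter not estimable, and 1 of 2 variance parameters identifiable. These results are algebraic and depend on no assumed effect size, SD or correlation. They do depend on Table 1 governing data collection, which the documents imply but other wording puts in doubt.

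The consequence is confined to this outcome's stated effect parameter and its within-subject variability. The randomised comparison of post scores remains available. The correction is still necessary, because the contradiction concerns the primary patient outcome and an uncollected baseline cannot be recovered.

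**What to change.** Make Study design, Study Procedures, Measures, Table 1, and Data analysis and sample size agree.

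- **Preferred.** Add the intention items to the survey completed before randomisation in both arms, mark Pre and Post for this row in Table 1, and state the step in Study Procedures. The planned interaction can then be fitted for each intention score. Name the score or scores: Measures item 2 assesses surgery and MOVE! intentions separately, Table 1 refers to three options, and the analysis text does not say which score enters the model. Baseline-adjusted ANCOVA is an option once a baseline exists, but is not needed to cure the defect.
- **If no baseline can be collected.** Replace the model with the between-arm difference in post scores and its 95% CI, and drop the within-subject variability aim for this outcome.
- **If some patients already lack a baseline.** Report the post-score difference for all patients, and within-subject variability only for those with both measures. The documents do not give enrolment status, but MOVE! visits were to be reviewed from May 2019 and the document is dated 02/12/2020, so this should be checked promptly.

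**Cost.** The preferred fix takes a few minutes of the 50-minute early-arrival slot. That slot already holds consent, the HIPAA form, the demographic survey and possibly the 18-minute video, and the documents do not show spare time. Measures item 2 can be read as five items in all or five per option, which affects the burden. Asking about intentions beforehand may sensitise patients, and not necessarily equally in both arms. The post-score fallback is a change of wording only.

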The goal of phase IIb interventions are to “determine whether a clinically significant benefit on the behavioral

risk factor can be achieved in a larger, more representative sample and whether this benefit is above and beyond the passage of time, nonspecific attention, or other treatment options.⁷ Successful execution of this component of the study will provide the results needed for phase III behavioral intervention testing in a subsequent, adequately powered, efficacy trial (for which an IIR will be submitted).

Creating an educational video for severe obesity care: The research team has reviewed the qualitative findings from Aim 1, identified the relevant codes and themes, and generated an 18 minute video regarding severe obesity treatment options within the VA. The video contains information about diet, exercise, and healthy behaviors, weight management medications, and bariatric surgery.

Study design: This is a randomized controlled trial comprising an intervention arm and a usual care arm. Patient outcomes will be assessed before and after Veterans observe the video according to the plan outlined in **Table 1**.

Study setting: The trial will occur at the Madison VA. The Madison West VA Clinic will be used as a recruitment site if recruitment at Madison VA is low.

Study population and recruitment: Veterans with severe obesity between the ages of 18 and 75 who are scheduled to attend an in-person MOVE! visit at the Madison VA will be identified via chart review (all upcoming MOVE! visits beginning in May 2019 within the Madison VA system). Recruitment will be extended to Madison-West clinic if recruitment at Madison VA is not sufficient. Patients who have had bariatric surgery, had a bariatric information session, or been referred for bariatric surgery within the last year will be excluded as well as patients with a positive pregnancy status/intention, illicit drug use, or who have a psychological or medical condition preventing them from meaningfully participating in our intervention. Patients who have participated in piloting the intervention will also be excluded. Those patients who do not speak English or do not have regular access to a telephone will also be excluded. Severe obesity will be defined as a body mass index > 35 in

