CPRS. Veterans will qualify as severely obese if their BMI is ≥ 35 within the last six months of being referred to MOVE!. Given that more than 300 severely obese patients were referred to the Madison VA MOVE! program annually, meeting our recruitment goal (up to 40) will require participation of 20% of severely obese patients over the course of a year.

Research staff will use CPRS, outpatient MOVE! appointment requests from CDW, and/or automated reports to identify Veterans with severe obesity between the ages of 18 and 75 who are scheduled to attend an in-person MOVE! visit at the Madison VA. Research staff will review upcoming MOVE! clinic appointments for eligible patients. Subsequent visits and subject eligibility will be assessed weekly. Eligible patients who have a MOVE! visit following 7 or more days of newly reviewed upcoming clinic visits will be sent a recruitment letter and/or email ahead of their visit with a brief explanation of the study inviting them to participate. The letter and/or email will state that the research team may call and/or email them up to 3 times over the next 3 months. Patients who agree to participate in the study over the phone, and who qualify for the study will be asked to arrive at their MOVE! visit 50 minutes early to go over the consent process and be placed into intervention/usual care arms.

Study Procedures:

Our researcher will meet each patient who has been recruited in a private room to go over the consent process. If patients are interested in participating in the study, they will be asked to sign a written informed consent to participate in the study as well as a HIPAA form to collect process measures. They will also complete a demographic survey.

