We aim to sequentially recruit up to 40 severely obese Veterans. Patients will be randomized to one of the two groups. Based on prior experiences from our co-investigator team and the literature on usability testing¹⁷ this sample size will be sufficient to assess feasibility and acceptability and seek evidence of signal regarding intervention effects. A power calculation will not be performed given that we are not evaluating statistical significance of the intervention at this point; rather, we are seeking an indication of clinically significant change, preliminary data on within- and between-subject variability in these measures, and evaluation of the feasibility of the study (cite A). Quantitative data will be analyzed using SAS version 9.3 (or higher) (SAS Institute, Cary, NC).

Data analysis approach: The digital audio recordings from all patient interviews will be transcribed by a transcriptionist who will be supported with CDA research funds. We will use a directed approach to content analysis,¹⁸ developing codes (descriptive labels) based on predetermined categories, such as those derived from interview questions. Any text that cannot be categorized with the pre-determined scheme will also be identified and categorized. Drs. [name] and [name] and our Researcher will analyze the first five patient transcripts. After analysis of the first patient transcripts, they will convene to adjudicate each coded phrase or idea. This procedure will be repeated for each subsequent transcript using the technique of constant comparison, ultimately developing a taxonomy of consensus codes.¹⁹ Each transcript will then be re-coded according to this coding scheme. Then higher-level coding will be conducted to identify themes and trends in the data to consolidate feedback for refinement of the analysis. The theme matrix technique²⁰ will be used to identify patterns in the data based on patient characteristics. Data will be managed and categorized using NVivo.

III. Data and Safety Monitoring Plan

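### The primary model needs a baseline intentions score that Table 1 does not schedule; once collected, that score is better used by adjustment than in a change-score contrast

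*Combined protocol and SAP*

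**What the plan says.** **Analysis.** Section II, Data analysis and sample size: "Analysis of the primary outcome will treat pre- and post-intervention outcomes as two repeated measures on each subject". Then: "The regression model will include a post-visit indicator, an intervention group indicator, and an interaction between the two". The interaction coefficient is named as the intervention effect, and "To account for the repeated measures within patient, the model will include a random patient effect". The model has no baseline covariate and does not constrain the arms to a common baseline mean.

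**Schedule.** Section II, Study design: "Patient outcomes will be assessed before and after Veterans observe the video according to the plan outlined in" Table 1. In Table 1 the row "Primary patient outcome: Behavioral intentions in pursuing any of the 3 treatment options in the VA" carries a single mark, under Post, for both arms. Demographics are marked under Pre only; recruitment and attendance rates are marked under both.

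**Procedures.** Before randomization, Study Procedures lists consent, a HIPAA form and one instrument: "They will also complete a demographic survey". Then: "Participants will then be randomized to the intervention or usual care arm with probability equal to 1/2". The Measures paragraph says that demographics are taken before the patient learns the assignment. It makes no such statement for intentions.

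**Size and purpose.** "We aim to sequentially recruit up to 40 severely obese Veterans". There is no power calculation and significance is not being assessed. The pilot seeks an indication of clinically significant change and estimates of variability, and it targets at least 80% retention. No SD or pre-post correlation is given.

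**The concern.** There are two linked problems, and the first must be settled before the second has any meaning.

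First, the model requires a measurement that the schedule does not contain. If staff work from Table 1 and the procedures list, no baseline intentions score will exist, and one cannot be recovered after the video or the MOVE! visit. The stated primary analysis would then have to be replaced after the data are in.

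Second, if the baseline is collected before assignment is revealed, randomization makes the two arms' baseline means equal in expectation. The planned model nevertheless estimates a separate baseline mean for each arm. This makes the effect a plain difference in changes and adds noise that adjustment would remove. The interval around the signal is one of the things this pilot hands to the later trial, so a wider interval than necessary has some cost.

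**Working it through.** **1. Can the planned model be fitted on the Table 1 schedule?** With post data only, the post-visit indicator equals 1 on every row, so it cannot be separated from the intercept. The interaction then equals the group indicator, so those two cannot be separated either. With one record per patient, the random patient effect cannot be told apart from residual error. The interaction is therefore not estimable. All that remains is a comparison of post scores.

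**2. What does the interaction estimate if a baseline is collected?** With two time points and complete data it is the difference between arms in mean change. A random-intercept model fitted to one simulated data set of 40 patients gave an interaction of -0.1302 and a difference in mean change of -0.1302.

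**3. Precision.** The plan gives no precision figure to reproduce. Inputs from the documents: up to 40 patients at 1:1, so n = 20 per arm; 80% retention gives 0.8 × 40 = 32, so n = 16 per arm. Assumed: equal pre and post variance, and correlation r = 0.3 to 0.7. In units of the outcome variance:

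- difference in change: 2(1 − r) × 2/n
- baseline-adjusted: (1 − r²) × 2/n
- ratio, adjusted to planned: (1 + r)/2
- post scores only: 2/n

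Estimating the baseline slope multiplies the adjusted variance by 1 + 1/(N − 4), which is 37/36 at N = 40 and 29/28 at N = 32.

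| r | SE planned (n = 20) | SE adjusted (n = 20) | Variance saved, large sample | N = 40 | N = 32 | SE saved, large sample |
|---|---|---|---|---|---|---|
| 0.3 | √0.140 = 0.374 | √0.091 = 0.302 | 35% | 33% | 33% | 19% |
| 0.5 | √0.100 = 0.316 | √0.075 = 0.274 | 25% | 23% | 22% | 13% |
| 0.7 | √0.060 = 0.245 | √0.051 = 0.226 | 15% | 13% | 12% | 8% |

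The SEs are in SD units and omit the slope correction. The post-only SE is √0.100 = 0.316, so below r = 0.5 the change contrast is less precise than ignoring the baseline. Simulation with the slope estimated (20,000 runs) gave savings of 33.5%, 22.3% and 12.3% at 20 per arm, and 33.7%, 21.9% and 12.9% at 16 per arm.

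**4. Sensitivity to the assumptions.** Over r = 0 to 0.9 with equal variances, the large-sample saving runs from 50% to 5%. If the post SD is k times the pre SD, the saving is 1 − k²(1 − r²)/(1 + k² − 2rk). Over r = 0.3 to 0.7 this is 50% to 37% at k = 0.8, and 22% to 2% at k = 1.25.

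**5. Would deleting the group term be enough?** A random intercept alone forces equal pre and post variance. The model then adjusts by b = 2rk/(1 + k²) rather than by the regression slope rk. At k = 1.25 and r = 0.7, b = 1.75/2.5625 = 0.683. The variance factor is k² + b² − 2brk = 1.5625 + 0.4664 − 1.1951 = 0.834. The planned change contrast has 1 + 1.5625 − 1.75 = 0.8125. The shortened model is thus about 3% worse than the plan (0.834/0.8125 = 1.026), while ANCOVA, at 1.5625 × 0.51 = 0.797, is about 2% better.

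**The case against.** The strongest case on the other side is that the planned model is a standard one, unbiased under randomization, and robust to unequal pre and post variances because it depends only on change scores. The pilot disclaims power and significance testing, and no decision rule uses this standard error. The model also reports change by arm and variance components directly, which the pilot wants. All of that stands, and it limits the second part to efficiency. It does not touch the first part, since the planned model also needs the missing baseline.

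It can also be said that Table 1 may have lost a mark when the PDF was read. That is possible, but the Pre and Post marks for demographics and for recruitment and attendance came through distinctly, and the procedures list independently names no baseline intentions questionnaire. Study design does speak of assessment before the video, but it defers to Table 1, so it does not settle the matter.

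Two stronger readings are tempting. A reader might infer that the plan definitely gives away 15% to 35% of its precision. The documents supply neither the correlation nor the variances behind that range, it is a variance figure rather than an interval width, and on the Table 1 schedule neither analysis can be run. A reader might also infer that any pre-score is taken before assignment is known, so that baseline means are equal by design. The documents say this of demographics only. A score taken after the assignment is revealed but before the video would also fit the text, and equal baseline means would then not be guaranteed.

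**Conclusion.** The concern holds in two parts of unequal weight.

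The main part is an internal conflict. The primary analysis requires pre and post intentions scores, while Table 1 (as extracted) and the procedures provide a post score only. As tabulated, the stated effect cannot be estimated. This conclusion needs no numerical assumption, only that the Table 1 marks were read correctly.

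The second part is conditional on a baseline being collected before assignment is revealed. With equal variances and r between 0.3 and 0.7, both assumed, adjustment reduces the variance by about 35% to 15% in large samples, by about 33% to 12% with 32 to 40 patients, and the standard error by about 19% to 8%. The gain shrinks at higher r or if the post SD exceeds the pre SD, and grows in the opposite cases. The planned contrast is not biased or invalid, so nothing beyond an efficiency gain should be claimed.

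**What to change.** 1. In Table 1, mark Pre for behavioral intentions. In Study Procedures, state that the items are completed with the demographic survey, before the assignment is revealed. The cost is about ten short items, reading the outcome description as five items each for surgery and MOVE!, within a session already planned.

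2. In Data analysis and sample size, replace the difference-in-change contrast with one of the following:
   - ANCOVA of the post score on arm and pre score; or
   - a repeated-measures model with a common baseline mean and an unstructured covariance, so that pre and post variances may differ.

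   Name one as primary. Do not simply delete the group term from the random-intercept model. The cost is a sentence or two of text and a small change to the SAS code.

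3. Keep per-arm mean change as a descriptive result, and report the estimated pre-post correlation and both SDs, so that the later trial can be planned from them.
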